9.2 Toxicity

10.0 Criteria for Removal from the Study

Subjects have the right to withdraw from the study at any time for any reason. An excessive rate of withdrawals can render the study uninterpretable; therefore, unnecessary withdrawal of subjects should be avoided. Should a subject decide to withdraw, all efforts will be made to complete and report the observations as thoroughly as possible. Criteria for discontinuation of therapy include:

- Clearly documented progressive disease (increasing requirement for blood transfusion, increasing spleen size, increasing platelet or white blood cell count, increasing frequency of phlebotomies, or frequency of thromboembolic events) or no response (see section 9.1) within 6 months from the start of the therapy on a given dose (i.e. continuously on the same dose level of PEG-IFN α -2a). **Caution:** Patient without response after 3 months on a given dose should have the dose escalated if possible (see section 6.2); if no response when on the escalated dose for 6 months, then therapy should stop.
- Severe toxicities not responding to dose adjustments (see section 6.2)
- Non-compliance to protocol requirements (see section 5.0)

- Development of other conditions for which, in the Investigator's opinion, it is in the subject's best interest to be withdrawn from the study.

11.0 Statistical Considerations

11.1 This is a phase II trial of PEG IFN-a2a (Pegasys®) as a treatment for ET and PV. In each disease, a response rate of 35% or more would be accepted as evidence for a good efficacy to be further pursued in this disease subsets in larger randomized or combination studies. Therefore, in each disease category, the study will stop if response is 07, < 1/11, <2/15. Otherwise it will accrue 80 patients to better define the response and toxicity profiles. Also, in the total study group, a severe toxicity rate of <20% is allowed. Therefore, the study will also stop if severe toxicity is observed in >7/15, 11/30, 15/45.

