4.11 Update of study results as of 01/15/2009 and plans

At present the study has accrued 40 patients with PV and 36 patients with ET. Most patients had extensive prior therapies with hydroxurea and anagrelide and all 40 patients with PV had phlebotomies. With a median followup of 24 months on Pegasys therapy, the overall hematologic response rate was 81% with PV (complete

in 78%) and 92% with ET (complete in 86%). These results are the best ever achieved with any form of therapy in PV and ET. In addition, measuring JAK2 V617F mutations, we observed complete molecular responses in 12% of patients and any molecular response in 53% of patients. Side effects were acceptable. At the Pegasys dose of 90 mcg weekly Grade 3 neutropenia was observed in only 8% of patients and other side effects (fatigue, dizziness, depression) in only 4% of patients each. These findings are a true therapeutic breakthrough in the management of PV and ET and have been also reproduced by investigators in France (Kiladjian et.al Blood 112;3065,2008) who reported with Pegasys therapy in 40 patients with PV a CHR in 78%, a complete molecular response in 24%, and a major molecular response in 69%.

Hoffman-LaRoche, the Company, declined to expand the study and provide free drug. Our results suggest this is the best available treatment for these patients. We would like to expand the study and continue therapy with Pegasys commercial preparation. We propose to include up to 100 patients with PV and 100 patients with ET. This will allow a more precise estimate of hematologic and molecular response with long term follow up, a better estimate of long term survival and toxicity profiles, and a treatment of patients on protocol which affords better care by our leukemia experts and allows future analyses of data in a large cohort including an evaluation of prognostic factors that determine molecular response and long term outcome. Our data was presented at ASH 2008 (Quintas-Cardama, Blood 112:653, 2008).

Update September, 2019

Sixteen patients remain on study for a median of 12 years (range 11 - 13). All patients are on a stable dose of pegylated interferon with normal blood counts. None of the patients have experienced drug-related adverse reactions in 9 years. Changes in the protocol reflect standard of care monitoring of patients in long term complete hematologic remission. This study represents the longest follow up of patients with ET or PV treated with pegylated interferon.

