6.2 Dose Escalation and Dose Reduction

Dose Level	Dose of Pegasys in micrograms SQ weekly
+4	450 mcg
+3	360 mcg
+2	270 mcg
+1	180 mcg
0(starting dose)	90 mcg
-1	45 mcg
-2	45 mcg every other week

Any patient who experiences grade 1 or 2 adverse event (see NCI-CTC guidelines, appendix C) should be maintained on the assigned dose if possible. Treatment should be put on hold if a patient experiences any of the following:

- grade 3-4 laboratory abnormalities
- grade 3-4 constitutional toxicity

Dose adjustments may be made at the discretion of the treating physician.

Questionable cases should be resolved by clinical judgment of the investigator.

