11.2 Update of statistical considerations as of 1/15/2009

Experience in 76 patients has shown very high response rates of 78% to 86% in ET and PV. This expansion of the study is to provide patients with the best available treatment, Pegasys, at an optimal dose schedule, in the context of a study using the commercial drug. Up to 100 patients with ET and 100 patients with PV will be treated. This will allow for 1) a large scale capture of more precise response data (hematologic, molecular), 2) detailed analysis of side effects, 3) evaluation of longer term prognosis and survival, and 4) analysis of potential prognostic factors associated with molecular response. Such analyses will be conducted using standard analytical methods.

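### No look at the 20% severe-toxicity limit is specified after patient 45, although 11.1 plans 80 patients and 11.2 permits 200

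*Combined protocol and SAP*

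**What the plan says.** Section 11.1 sets a limit for both diseases pooled: "Also, in the total study group, a severe toxicity rate of <20% is allowed". It applies the limit at three sample sizes: "Therefore, the study will also stop if severe toxicity is observed in >7/15, 11/30, 15/45". The > sign is printed once, before the first count. The same section plans further accrual: "Otherwise it will accrue 80 patients to better define the response and toxicity profiles". It does not say whether 80 is per disease or in total; either figure exceeds 45.

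Section 11.2 (2009) raises the ceiling: "Up to 100 patients with ET and 100 patients with PV will be treated". It lists a detailed side-effect analysis among the purposes of the expansion, by unspecified standard methods, and gives no toxicity look, count or limit. Section 4.11 gives the position at that time: "At present the study has accrued 40 patients with PV and 36 patients with ET".

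The other safety provisions in the text supplied act on single patients or concern reporting. Section 6.2 covers grade 3-4 laboratory and constitutional events: "Treatment should be put on hold if a patient experiences any of the following". Section 10.0 ends therapy for severe toxicities that do not respond to dose adjustment. Section 12.1 has SAEs reported under institutional policy and points to Appendix G, which was not supplied. Section 9.2 (Toxicity) has a heading but no text.

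**The concern.** The plan names a limit for the whole study group but says how to check it only for the first 45 patients. Followed as written, it could fill most of its permitted places while the true severe-toxicity rate exceeds 20%, with no further count at which anyone must compare the data with that limit. This would matter little if passing the look at patient 45 were strong evidence of a rate below 20%, so the sensitivity of the three looks has to be checked. Toxicity is the secondary objective (2.2) and side effects are a stated purpose of the expansion.

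**Working it through.** **Inputs.** From 11.1: limit 0.20; looks at n = 15, 30, 45 with counts 7, 11, 15. From 4.11: 40 PV + 36 ET = 76 accrued. From 11.2: ceiling 100 + 100 = 200. The documents give no error rate or method for the toxicity rule.

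**1. Reproducing the printed counts.** Take the smallest r with P(X ≥ r | n, 0.20) ≤ 0.05, X binomial.

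| n | r | P(X ≥ r) | P(X ≥ r − 1) |
|---|---|---|---|
| 15 | 7 | 0.018 | 0.061 |
| 30 | 11 | 0.026 | 0.061 |
| 45 | 15 | 0.025 | 0.052 |

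This gives 7, 11, 15 exactly. So does stopping when Pr(rate > 0.20) > 0.97 under a Beta(0.4, 1.6) prior. The printed counts therefore do not identify the criterion.

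**2. Coverage.**
- Patients after the last look: 200 − 45 = 155, and 155/200 = 77.5%.
- Of these, 76 − 45 = 31 were already enrolled at the 2009 update.
- Expansion places: (100 − 40) + (100 − 36) = 60 + 64 = 124.

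**3. Sensitivity of the three looks.** Exact recursion: carry the binomial distribution of the cumulative count from look to look, removing paths that reach the boundary. Chance of ever stopping:

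| True rate | ≥7, ≥11, ≥15 | ≥8, ≥11, ≥15 (> at first look only) | ≥8, ≥12, ≥16 (> at all looks) |
|---|---|---|---|
| 20% | 4.8% | 4.0% | 1.8% |
| 25% | 18.3% | 16.9% | 9.8% |
| 30% | 42.7% | 41.2% | 29.0% |
| 35% | 69.3% | 68.3% | 55.9% |

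At a true 30% the study passes every look with probability 1 − 0.427 = 57% to 1 − 0.290 = 71%. The last look is passed with 14/45 (31%) on any reading, and with 15/45 (33%) if > applies there.

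**4. What continued looks could do (illustration).** The count starts at zero with the first expansion patient; looks at 30, 60, 90 and 120. The look spacing and both criteria are assumptions.

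| Criterion | Stop at or above | True 20% | 25% | 30% |
|---|---|---|---|---|
| Beta(0.4, 1.6), 0.97 | 11/30, 19/60, 26/90, 33/120 | 6.5% | 37% | 80% |
| Exact tail ≤ 0.05 | 11/30, 18/60, 25/90, 32/120 | 9.4% | 46% | 85% |

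Under the first row, at a true 30%, an average of 78 of the 124 places would be used.

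**5. Pooled looks depend on the first 76.** The severe-toxicity count in the first 76 is not reported, so a range is assumed. With Beta(0.4, 1.6) looks every 15 patients from 90 to 195 and 30% in the expansion, the chance of stopping is 5% after 6/76, 32% after 12/76, 57% after 15/76 and 80% after 18/76. With 6/76 the expected total-group rate at 200 is (6 + 0.30 × 124)/200 = 21.6%, so rare stopping is what a total-group rule should then show.

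**The case against.** The strongest reply is that early looks followed by a descriptive expansion are a legitimate phase II choice. It was made after 76 patients with a median follow-up of 24 months, using a commercial drug, with patient-level holds and discontinuation in place. Nothing in the objectives makes 20% a hypothesis to be tested at the end. This stands as far as it goes: the design is not invalid. But 11.1 states the limit for the total group, and 11.2 does not say that the looks were meant to end or why.

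A reader might answer that toxicity was known to be low: "At the Pegasys dose of 90 mcg weekly Grade 3 neutropenia was observed in only 8% of patients". The documents do not support that step. Section 4.11 gives selected events at one dose level, without a denominator or an overall severe-toxicity rate, so the figures cannot be set against the 20%.

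A reader might also go too far the other way and infer that the study had no safety monitoring, or that the limit lapsed at patient 45. Neither follows. The sentence in 11.1 has no end point, and 6.2, 10.0 and 12.1 still apply. What is missing is a specified numeric check, and only in the text supplied.

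The objection that the matter is largely moot has real weight. The 2019 update says: "Sixteen patients remain on study for a median of 12 years (range 11 - 13" years). That puts their entry at roughly 2006 to 2008, or early 2009 allowing for rounding, essentially before the expansion. It describes only those still on study, however, and does not state that accrual closed or how many joined after the 76th.

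Finally, severe toxicity is not defined for the rule and treatment is open-ended, so a count of patients ever affected rises with exposure. Further looks need a definition and an observation window as well as counts.

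**Conclusion.** The point holds in a limited form. In the text supplied, no numeric check of the 20% limit is specified after patient 45, that is, for up to 155 of 200 permitted patients and up to 124 expansion places. Passing the three looks is weak reassurance, since at a true 30% it happens 57% to 71% of the time. That range describes the existing looks and assumes independent patients with a constant rate; it does not measure harm after patient 45.

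A reader might infer that 124 or 155 patients were treated above the limit. The documents do not support this: the numbers are ceilings, actual enrolment in the expansion is not given, and no overall severe-toxicity rate is reported. Nor can a rule in Appendix G or under 9.2 be excluded.

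The point should be fixed if accrual is open. It is minor, a matter of reporting, if accrual is closed.

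**What to change.** **In either case.** State in 11.1 which inequality applies at each of the three looks.

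**If accrual is open.** State in 11.2 that looks against the 20% limit continue through the expansion, in the total study group as 11.1 defines it and, as a supplementary check, among expansion patients alone. Give one definition of severe toxicity and a fixed observation window per patient. The sponsor should calibrate the boundaries and report their operating characteristics; the counts in step 4 are illustrations only. The cost is a short protocol text, the definition and window, and a count at each look, with no added patients. The downside is the chance of stopping at an acceptable rate: 6.5% to 9.4% at exactly 20% under the two expansion-only illustrations, to be recalculated for the combined scheme.

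**If accrual is closed.** Report the severe-toxicity rate with its exact 95% interval against 20%, for all patients and for those after the 76th, and state that no look was specified after patient 45. For scale, if all 124 places were filled, the interval would lie wholly below 20% with at most 15/124 (12.1%; 6.9% to 19.2%) and wholly above it with at least 35/124 (28.2%; 20.5% to 37.0%). This has no operational cost.

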11.2 Update of statistical considerations as of 1/15/2009

Experience in 76 patients has shown very high response rates of 78% to 86% in ET and PV. This expansion of the study is to provide patients with the best available treatment, Pegasys, at an optimal dose schedule, in the context of a study using the commercial drug. Up to 100 patients with ET and 100 patients with PV will be treated. This will allow for 1) a large scale capture of more precise response data (hematologic, molecular), 2) detailed analysis of side effects, 3) evaluation of longer term prognosis and survival, and 4) analysis of potential prognostic factors associated with molecular response. Such analyses will be conducted using standard analytical methods.

12.0 Reporting Requirements

12.1 Serious Adverse Events will be reported per institutional policy. Adverse events will be reported in the medical record.

See Appendix G

12.2 **The research protocol includes adequate plans to protect identifiers from improper use. HIPAA Identifiers (name, medical record number)**

will be collected but will be replaced by study numbers in the analytical file; complete confidentiality will be maintained during this retrospective evaluation, manuscript preparation, and submission.

(a) The research protocol includes an adequate plan to destroy the identifiers at the earliest opportunity consistent with conduct of the research. Identifiers (name, medical record number) will be collected but will be replaced by study numbers in the analytical file; Complete confidentiality will be maintained during this retrospective evaluation, manuscript preparation, and submission. Identifiers will be destroyed within 1 year of publication

(b) The research protocol includes adequate written assurances that the PHI will not be reused or disclosed to any other person or entity, or for other research.

Complete confidentiality will be kept during this retrospective evaluation, manuscript preparation, and submission. This data will not be used for any other purpose and will not be reused or disclosed to any other person or entity, or for other research.

Anonymized information will be retained by the investigator in locked files or password protected databases

2. The research could not practicably be conducted without access to and use of the PHI. Access and use of PHI is essential to conducting this study and meeting the study objectives.

